### **6.1 Primary study parameter(s)**

Our primary outcome is a dichotomous composite score ( yes / no MCID improvement in health-related quality of life or quality of healthcare), which is based on the scores of PROMIS dimensions (GPH, GPM) and the P3CEQ-score.

To test the effect of the intervention over time, we use a three level multilevel logistic model. A model with time , group (intervention or control) and the interaction between time and group will be performed. With this model we can test the effect of the intervention during the entire study period and the intervention effects at 6 months and at 12 months.

In a mixed model both fixed and random effects can be analyzed. We perform a model with random effect for practice and patients. All other variables will be held fixed. Covariates included in the analyses will be age, sex, smoking status, education level, and social support.

### **6.2 Secondary study parameter(s)**

The relationship between treatment and secondary outcome measures measured at 6 and 12 month follow up will be analysed with mixed three level linear or logistic regression, taking into account that the times of measurement (after 6 and 12 months) are clustered within patients, and patients within general practices. A model with time, group (intervention or control) and the interaction between time and group will be performed. Covariates included in the analyses will be age, sex, smoking status, education level, and social support

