## **4. METHODS**

### **4.1 Study parameters/endpoints**

Outcome measurement will be based on the quadruple aim framework.[16] To measure population health we will assess quality of life, self-management, and disease-specific physiological factors. Our composite primary outcome will be health-related quality of life *and* patient experience, measured with the PROMIS Global 10 and P3CEQ, as described in paragraph 2.4. Secondary outcomes will be: self-management, measured with the Dutch short version of the patient activation measure (PAM-13).[17] Measurement of disease-specific physiological factors will take place as part of routine care in both study groups and include blood pressure, body mass index (BMI), cholesterol, blood glucose levels and lung function parameters, if applicable. All outcomes will be measured at baseline, 6 months, and 12 months follow-up. Physiological factors will be recorded in the electronic medical records as part of routine care and will be extracted from 3 months before baseline until 12 months follow-up. Also, healthcare utilisation and prescription data will be extracted from the electronic medical records at the end of follow-up. Health care provider experiences will be measured with an appropriate self-reported experience measure.

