#### **4.1.2 Secondary study parameters/endpoints (if applicable)**

- PROMIS dimension GPH score
- PROMIS dimension GPM score
- P3CEQ-score

- Patient Activation Measure (PAM)
- EQ-5D-5L
- Health care use according to Medical Consumption Questionnaire
- Health care use according to general practice data
- Body weight, BMI, smoking status, HbA1c, glucose, cholesterol levels and blood pressure from general practice data (registered for normal care).
- Experience of healthcare providers on COPILOT and MAS-GZ questionnaire

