### 4.3 Study procedures

#### Population health

Category	Measurement instrument	Time
Health related quality of life	EQ-5D-5L	Baseline, 6, 12 months
Self-management	Patient Activation Measure (PAM)	Baseline, 6, 12 months
Health related quality of life	PROMIS GLOBAL-10	Baseline, 6, 12 months
Unscheduled healthcare	Data from medical records	12 months
Physiological parameters	Data from medical records	12 months

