#### Cost-effectiveness

Category	Measurement instrument	Time
Medication	Data from medical records	12 months

Scheduled and unscheduled healthcare utilisation	Data from medical records	12 months
Referrals	Data from medical records	12 months
Costs	Data from medical records	12 months
	Medical consumption questionnaire	Baseline, 3, 6, 9, 12 months
	EQ-5D-5L	Baseline, 6, 12 months

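### Record-based health care use has no stated observation window, no look-back and no suitable effect model in section 6.2

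*Combined protocol and SAP*

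**What the plan says.** Section 4.1.2 lists "Health care use according to general practice data" as a secondary endpoint.

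The timing statements differ:
- Section 4.1 says that "healthcare utilisation and prescription data will be extracted from the electronic medical records at the end of follow-up". It gives no start date, look-back or division into periods.
- Just before that, the same section gives physiological factors an explicit window: they "will be extracted from 3 months before baseline until 12 months follow-up".
- Section 4.1 also says, without exception, "All outcomes will be measured at baseline, 6 months, and 12 months follow-up".
- The population health table in section 4.3 reads "Unscheduled healthcare Data from medical records 12 months". The cost-effectiveness table there has a row for "Scheduled and unscheduled healthcare utilisation", also from medical records at 12 months only.

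For the analysis, section 6.2 says that "secondary outcome measures measured at 6 and 12 month follow up will be analysed with mixed three level linear or logistic regression", and adds: "A model with time, group (intervention or control) and the interaction between time and group will be performed". The covariates are age, sex, smoking status, education level and social support. No count model, exposure time or earlier value of the outcome is named.

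**The concern.** Consultations, referrals, prescriptions and unscheduled contacts are counts accumulated over a period. They are usually skewed, and the period can differ between patients. A model with times nested in patients and a time-by-group term needs at least two occasions per patient, and the plan does not say that this endpoint has two.

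Practices also differ in how often they see, refer and prescribe for patients. With few practices, the arms can differ by chance in these habits before the programme starts. The records that supply the outcome would normally also show earlier use, but the plan does not ask for it.

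At stake are the precision of this endpoint and the freedom to choose its model after the data have been seen.

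**Working it through.** **The plan's own figures.** The documents give no number for record-based use. The total of 680 in section 2.4 concerns the primary outcome. It reproduces as 138 per arm for 20% v 35%, design effect 1 + 31 × 0.03 = 1.93, and 276 × 1.93 / 0.8 ≈ 666, rounded up to 17 practices of 40. It has no bearing on this point.

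**Step 1: can the 6.2 model be fitted?** The fixed part has four columns: intercept, time, group, time × group.
- *One total per patient.* Time is constant, so it duplicates the intercept, and time × group duplicates group. The rank is 2 of 4. In the linear version the patient intercept cannot be separated from residual error, because only their sum is identified.
- *Two periods (0–6 and 6–12 months).* The rank is 4 of 4 and the structure is estimable. The linear or logistic form remains, and so does the absence of an exposure term.
- *6.2 read as covering only outcomes measured at both 6 and 12 months.* Record-based use is then outside it. Section 6.3 totals costs per group and divides by patients and length of follow-up; it gives no effect model for use.

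**Step 2: observation time.** Section 6 includes data up to the point of dropout, and section 2.4 allows for 20% loss. That 20% is loss from questionnaire follow-up in the pilot, so loss from records may be smaller. Section 6.2 makes no provision for either.

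**Step 3: what the missing prior use costs.** All inputs here are assumptions except the practice numbers, 10 v 5 from section 4.2 (10 v 10 if the five control practices from the parallel trial are counted), and the patients per practice.

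Closed form, in outcome SD units, with m = 32 patients per practice (40 less 20%):
- Unadjusted variance of the arm difference = [ICC + (1 − ICC)/m] × (1/10 + 1/5).
- Adjusted variance = [ICC(1 − r_c²) + (1 − ICC)(1 − r_p²)/m] × (1/10 + 1/5), where r_c and r_p are the practice-level and patient-level correlations of prior use with the outcome.
- At ICC 0.03, unadjusted: (0.03 + 0.97/32) × 0.3 = 0.0181, SE 0.135. At ICC 0.10, SE 0.196.

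| r_c / r_p | Variance removed, ICC 0.03–0.10 |
|---|---|
| 0.5 / 0.5 | 25% |
| 0.7 / 0.5 | 37–44% |
| 0.9 / 0.7 | 65–74% |

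The SD of the chance difference between arms in practice habit is √[ICC × (1/10 + 1/5)] = 0.095–0.173 outcome SD. With 10 v 10 it is 0.077–0.141.

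Simulation of counts (1,500 trials per scenario; mean 8 contacts a year, between-practice SD 0.1–0.3 on the log scale, practice correlation 0.8, patient correlation 0.5–0.7, 40 patients per practice, 10 v 5 practices): adjusting for the practice mean of the previous year removed 17–56% of the variance. The SE was 9–18% of the mean before adjustment and 8–13% after. A second run with 3,000 trials per scenario gave 21–56% at 10 v 5 and 25–56% at 10 v 10.

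**Step 4: is it bias?** Null simulation of 4,000 trials (mean 6 contacts, practice log-SD 0.25, 10 v 5 practices, 32 patients each), comparing practice means:

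| Analysis | Mean difference | SD | Type I error |
|---|---|---|---|
| Unadjusted | 0.02 | 0.98 | 4.2% |
| Adjusted for prior use | 0.00 | 0.35 | 4.9% |

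Both are centred on zero with type I error near 5%. The fall in SD is a favourable extreme, because each patient's underlying rate was held the same in both years. This run serves only to check bias.

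**The case against.** Three stronger readings are tempting, and the documents support none of them.

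1. *The outcome is a single 12-month count, so the model fails.* The documents give an extraction time, not an aggregation rule. Physiological parameters carry the same 12-month entry in section 4.3 although they span 3 months before baseline to 12 months, so the entry may only be the extraction date. Section 4.1 also claims three time points for all outcomes. The model fails on one reading only.

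2. *Section 6.2 prescribes a wrong model for this outcome.* Its sentence is limited to outcomes measured at 6 and 12 months. If use is recorded at 12 months only, the fault is a missing model, not a misfitting one.

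3. *The result is biased, or is mainly a contrast of practices' habits.* Practices are randomised, stratified by cooperative and by socioeconomic status of the practice population (section 4.2), and practice is a level of the model. Step 4 shows no bias. At the lower end of the range, adjustment removes only 17% of the variance.

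Other limits also stand. The precision figures rest on assumed inputs and compare practice means. They do not test the negative binomial model, and they put no size on the harm from a linear form. Section 4.3 schedules the medical consumption questionnaire at baseline and repeatedly, so self-reported use is not affected. Costs are analysed under section 6.3, not by this model.

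What survives is that no reading of the plan gives this endpoint a stated window, a count model, an exposure term and a prior-use covariate. The general sentence on three time points does not repair this: it conflicts with the section 4.3 tables, and section 6.2 uses no baseline value.

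**Conclusion.** The point holds as a specification gap with an inexpensive improvement attached, and it is limited to record-based health care use. Depending on the reading, the 6.2 model cannot be fitted, can be fitted but treats counts as linear or binary and ignores observed time, or does not apply. On all three readings prior use is not adjusted for, and no window for it is stated.

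The cost is precision and chance imbalance between arms with 15 to 20 practices, not systematic bias. Under the simulated assumptions, adjustment removes roughly 17–56% of the variance of the arm difference; the closed form gives 25–74% under its own. The true gain depends on the between-practice variation and the year-to-year correlation of use, neither of which the documents report. No sample size depends on this.

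**What to change.** 1. Reconcile the timing statements in section 4.1 with the section 4.3 tables. State the period that record-based use covers, and whether it is one total or split at 6 months.
2. Extract the same utilisation and prescription items for a fixed period before baseline, for example 12 months, in the same query. First check that consent covers that period.
3. In section 6.2, analyse record-based counts with a negative binomial mixed model: patients within practices, log of observed months as offset, adjusted for prior use. Add a period level only if the records are split at 6 months.
4. Keep the three-level model for questionnaire scores.

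The cost is a wider date range in an extraction already planned, a consent check, and a few lines of analysis-plan wording. It should be settled before the records are extracted, so that the model is not chosen after seeing the data.

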### **6.3 Cost analysis**

We will perform two different approaches for cost analysis. First, we will assess total costs per capita per month (triple aim measure). Total costs will be calculated from a healthcare and a societal perspective. The healthcare perspective includes all costs covered by the healthcare budget, i.e. medication prescriptions, contact with care providers (GP, medical specialist, nurse, physiotherapist, dietician, podiatrist, occupational therapist), home care, hospital admissions, emergency department visits and rehabilitation. The costs from the

societal perspective include travel costs and costs of productivity loss due to absence from paid work. Total costs will be calculated per group and then divided by the number of patients per group and the length of follow-up to assess the total costs per capita per month. Data on healthcare utilization and medication prescriptions will be extracted from the electronic medical records of the participating general practices. Additional data on healthcare utilization as well as data on travel costs and absence from paid work will be retrieved from patients by questionnaire at 6 and 12 months. In addition, we will conduct a cost-effectiveness analysis in which cost-effectiveness will be assessed in terms of costs per quality-adjusted life years (QALY). QALYs will be based on the EuroQoI-5D (EQ-5D) utility values using the Dutch value set.

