**Intervention:** a GDM programme including person-centered and holistic care. This programme will replace the SDM programmes for DM2, COPD and CVD that are currently used in the participating primary care cooperatives.

**Main study parameters/endpoints:** effectiveness will be evaluated by Quadruple Aim outcomes at baseline, at 6 months, and at 12 months follow-up by comparing changes in the intervention group with the comparator group. Patient experiences will be measured with the P3CEQ questionnaire. Population health will be measured with the PROMIS Global-10 questionnaire. Self-management will be measured with the Patient Activation Measure (PAM) score. Healthcare professional experiences will be measured with the MASGZ and the COPILOT questionnaire. Data for calculating costs and conducting a cost-effectiveness analyses will be measured by the Medical Consumption questionnaire and the EQ-5D questionnaire and by process outcomes such as the number and type of consultations and referrals, and duration of consultations from the Electronical Medical Files. At 12 months, a purposive sample of patients and professionals will participate in focus group interviews to collect information on experiences and facilitators and barriers for further implementation. Also, the competences needed by the healthcare professionals to provide personalised and integrated chronic care will be explored.

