## 2. STUDY DESIGN

We will perform a cluster randomized controlled trial with a follow-up time of 12 months.

The three participating primary care cooperatives, i.e. Nijmegen, Arnhem, and Doetinchem, will recruit 15 general practices (clusters) who will be randomized using a 2:1 ratio in two study groups:

1. The intervention group: the GDM programme including a person-centered, integrated, and holistic approach
2. The control group: care as usual according the current SDM programmes

All practices will receive instructions from the research team on the procedures of the evaluation study. Participating practices will then start recruiting patients from a random sample of eligible patients, i.e. patients with DM2, COPD, or CVD who are currently receiving SDM. After written informed consent, information will be collected through questionnaires at baseline, 6 months and 12 months, and by interviews and data collection from electronic medical records. Information will also be collected from the participating healthcare providers through questionnaires and interviews.

In the two months prior to the start of the intervention, all practices in the intervention group will be trained in providing GDM by their own primary care cooperative. During follow-up two to three intervention meetings will take place including peer coaching and case study discussions.

Practices who are allocated to the usual care group will not receive any training, but will continue with their SDM programmes.

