### 3. TREATMENT OF SUBJECTS

#### 3.1 OPTIMA FORMA intervention

The core of GDM programme including person-centered and holistic approach is a cyclical process described in Figure 1. The practice nurse in the general practice will act as case manager. She/he can consult the general practitioner or other health providers when necessary. The first step in the intervention is assessing the integral health status of the patient (health across multiple domains, including physiological measurements and symptoms of disease), using a (preferably digital) questionnaire at home and physical measurements. The second step is an appointment in which the results are discussed with the patient in a semi-structured way. The case manager discusses if the results are recognizable, if there are other issues which haven't come up, and the priorities of the patient. Personal goals are formulated in the third step, which can range from purely medical goals to social goals. In the fourth step, the healthcare professional and patient will choose through shared-decision making the most appropriate interventions and support to achieve these goals. The goals and interventions are documented in a personal healthcare plan, which is preferably digitally available for all relevant healthcare professionals and the patient. Next, referrals are made if necessary and the treatment is started. An evaluation is planned and carried out, if necessary multiple times. If a treatment goal is reached or another treatment goal is more urgent, the cycle can be repeated.

[figure not shown]

Figure 1. Presentation of the cyclic process of the GDM programme

In order to provide the OPTIMA FORMA intervention to participating patients all healthcare professionals involved will be trained by their primary care cooperative on the concept of Positive Health, communication skills, use of materials and ICT, and interprofessional collaboration prior to the start of the intervention. During follow-up, the

practices will receive additional support from the primary care cooperative through intervision meetings and case report discussions.

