### **3.2 Usual care**

Practices in the control group provide care as usual, which consists of the SDM programmes according to the national care standards and General Practice guidelines (NHG) for DM2, COPD and CVD. According to these protocolised programmes, patients with COPD, CVD or DM2 visit their general practice at a standard frequency per year (1 – 4 times) and standard monitoring measurements and topics are discussed.

The practices that are randomised to the control group will not receive any additional training related to this study.

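### Section 6.3 has no cost item for the GDM training and intervision meetings that only intervention practices receive, so that arm's cost will be understated, by an amount the documents do not determine

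*Combined protocol and SAP*

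**What the plan says.** Section 6.3 (Cost analysis) plans two outputs: total cost per capita per month, and cost per QALY. It defines the healthcare perspective as follows: "The healthcare perspective includes all costs covered by the healthcare budget, i.e. medication prescriptions, contact with care providers". The list goes on to name the types of provider and ends with "home care, hospital admissions, emergency department visits and rehabilitation". The "societal perspective include travel costs and costs of productivity loss due to absence from paid work". The first output is formed thus: "Total costs will be calculated per group and then divided by the number of patients per group and the length of follow-up". Resource use comes from general practice records and from patient questionnaires. The cost-effectiveness table in section 4.3 likewise names only medical records, the medical consumption questionnaire and the EQ-5D-5L.

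The programme has inputs of another kind. Section 2 (Study design) says that, in the two months before the start, "all practices in the intervention group will be trained in providing GDM by their own primary care cooperative", and that two to three meetings with peer coaching and case discussion take place during follow-up. Section 3.1 adds that "practices will receive additional support from the primary care cooperative through intervision meetings and case report discussions"; I take these to be the same meetings. For the comparator, section 3.2 says: "The practices that are randomised to the control group will not receive any additional training related to this study".

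On consultations, the Summary counts their number and type among the data for calculating costs, "and duration of consultations from the Electronical Medical Files".

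**The concern.** Cost-effectiveness is one of the four aims of the study. Training and intervision use paid time of practice staff and of the cooperatives' trainers, and they occur in one arm only. If the stated list is followed, that time is counted nowhere, and the intervention arm looks cheaper than it is. Nothing else in 6.3 offsets this.

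These are costs of the programme, not of the research. The cooperatives deliver the training and intend to introduce GDM whether or not the trial is run (Summary and section 7.3). Section 7.5 says the training will be offered to other care organisations if GDM proves effective, and that insurers and policy makers are among the audiences for the results. Organisations that adopt GDM would have to bear this cost.

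**Working it through.** **Step 1. Is the item missing?** The plan states no programme cost, unit price or expected cost difference, so there is no figure to reproduce. The check is a comparison of sections.

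| Programme input | In the 6.3 lists? | In the 4.3 cost table? | Arm |
|---|---|---|---|
| Training before the start (sections 2, 3.1) | No | No | Intervention only |
| Two to three support meetings (sections 2, 3.1) | No | No | Intervention only |
| GP and nurse contacts | Yes | Yes, as healthcare utilisation | Both |
| Consultation duration | Not mentioned | Not mentioned | Both; the Summary names it as cost data |

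The list in 6.3 is introduced by 'i.e.', so it defines the costs and does not merely give examples. Even if the opening phrase about the healthcare budget is read broadly, the only named sources are patient-level records and patient questionnaires. Neither would be expected to hold professionals' training or meeting hours. Training also precedes the start, while the formula divides by length of follow-up, so without a rule this one-off cost falls outside the costing window.

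**Step 2. How does the omission enter the endpoint?** From the 6.3 formula:

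understatement per patient per month = C / (n × 12)

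where C is the uncounted cost per practice and n is the number of patients over whom it is spread. The documents give about 40 recruited patients per practice (Summary) and 12 months (section 2). They do not give C. For C = EUR 1,000 and n = 40, the result is 1,000 / (40 × 12) = EUR 2.08 per month, or EUR 25 per patient-year.

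**Step 3. Range under assumed programme costs.** The values of C and the 400 programme patients per practice are assumptions.

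| Assumed C per practice (EUR) | n = 40 study patients (EUR per patient per month) | n = 400 programme patients (EUR per patient per month) |
|---|---|---|
| 2,000 | 4.17 | 0.42 |
| 5,000 | 10.42 | 1.04 |
| 10,000 | 20.83 | 2.08 |
| 20,000 | 41.67 | 4.17 |

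**Step 4. Range built up from staff time.** Assumed: 3 to 6 professionals per practice, 8 to 24 hours each for training plus meetings, and EUR 50 to 100 per hour. Trainers' time is not included.

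- Low: 3 × 8 × 50 = EUR 1,200. Over 40 patients this is EUR 30 each (EUR 2.50 per month); over 400 it is EUR 3 each (EUR 0.25 per month).
- Middle: 4 × 16 × 70 = EUR 4,480. Over 40 patients this is EUR 112 each (EUR 9.33 per month); over 400 it is EUR 11.20 each (EUR 0.93 per month).
- High: 6 × 24 × 100 = EUR 14,400. Over 40 patients this is EUR 360 each (EUR 30 per month); over 400 it is EUR 36 each (EUR 3 per month).

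Moving from 40 to 400 patients changes every figure tenfold. Within these assumptions, the allocation rule matters about as much as the cost itself.

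**The case against.** **Longer consultations.** A reader might infer that the extra time of GDM consultations is also left out. The documents do not support this. Section 6.3 costs GP and nurse contacts, the Summary names duration as cost data, and nowhere is it said that GDM consultations are longer or more frequent. What remains is an unstated rule: 6.3 does not say whether a contact is valued by its length or at a flat price. A flat price would miss extra time, if there is any.

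**No delivery cost at all.** A reader might also infer that the intervention arm is charged nothing for delivering GDM. That goes too far. Under section 3.1 the programme is delivered largely through nurse appointments, consultation with the GP and referrals, and contacts with care providers are costed in both arms. The gap is training and peer support.

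**Support, materials and ICT.** The cooperatives also organise the SDM programmes that GDM replaces, and 6.3 lists no SDM overhead either. The net difference is unknown. Charging these inputs in full to GDM could create the opposite bias, so only the increment belongs in the comparison.

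**Costing scope.** The documents do not say who pays for the training. A running-cost comparison that leaves out one-off set-up can be defended if it is declared. Section 6.3 neither declares nor justifies that choice, and the argument is weaker for meetings held during follow-up.

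**Size.** All inputs to the range are assumed, and spread over the whole chronic-care list the effect may be small. No total cost or expected cost difference is given, so nothing shows that a conclusion would change. This limits what can be said about size, but not about direction.

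**Conclusion.** The point holds for training and intervision. They are absent from every cost list, no planned source captures them, and only intervention practices receive them. Cost per capita per month will therefore understate the intervention arm's cost. Cost per QALY will do the same if it uses the same totals, which 6.3 implies but does not say.

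The size cannot be derived from the documents. The only firm arithmetic is EUR 2.08 per patient per month for each EUR 1,000 per practice, given 40 patients and 12 months. The assumed inputs above run from about EUR 0.25 to about EUR 42 per patient per month, and the low end may be unimportant.

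This is more than a missing detail, because following the list as written gives a one-sided result on a stated aim. It does not touch the composite primary outcome, the randomisation or the sample size.

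**What to change.** 1. Add to 6.3 a cost item for the GDM programme, charged to the intervention arm: hours of training and intervision, covering both the professionals' and the trainers' time, taken from the cooperatives' records. Name those records as a source in the 4.3 cost table. It is best to start the record prospectively, since no planned source holds these hours.
2. Pre-specify how the one-off training cost is allocated: base case over all programme patients in the practice, one sensitivity analysis over study patients only, and one excluding set-up cost.
3. Include cooperative support, materials and ICT only as the increment over the SDM programmes being replaced.
4. State in 6.3 that practice contacts are valued using the consultation duration already listed in the Summary, and add duration to the 4.3 cost table.
5. State that the cost per QALY uses the same cost totals.

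The cost of the change is some SAP wording and a short cost record from three cooperatives. The reported cost result will be somewhat less favourable to GDM.
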